4.1 Inclusion Criteria

The study will include provider subjects for intervention and analysis and patient-subjects for analysis. The study criteria are defined below.

In order to be eligible to participate in this study, providers must meet all of the following criteria:

1. Intern practicing on the general internal medicine service at Brigham and Women's Hospital (including Faulkner)
2. Assigned to the “twilight” team
3. Consent to participate
4. Not previously identified for this study

Patients who meet the following criteria will be included in the analysis:

1. Adults ≥ 65 years

2. Admitted to the BWH/BWFH general medicine service under the care of one of the consenting interns (specifically, with the intern listed as the “Responding Clinician”)

4.2 Exclusion Criteria

Our study population will be restricted to adult subjects (≥ 65 years) who were not on the high-risk medication of interest before admission. The specific age range was selected because clinical guidelines for high-risk prescribing for the medications of interest are clearer for this age range, and because overprescribing is a well-documented issue in older patients. Patients who were previously on the medication of interest before their present admission will be excluded because of potential withdrawal concerns. To enhance generalizability, we will not apply any additional exclusion criteria.

4.3 Recruitment and retention

As described in Section 3.2, BWH uses 2-week service blocks for its inpatient general medicine evening (twilight) coverage, and at the beginning of each block, we will identify the interns assigned to twilight teams (i.e., the primary prescribers on the general medicine service team) one week prior to their service. We will focus on interns from the “twilight” (i.e., evening) teams as they cover the shifts during which the high-risk medications of interest (specifically anti-psychotics, benzodiazepines, and sedative hypnotic “Z-drugs”) are typically first initiated. In addition to being the least experienced physicians on the medical team, they are also the first and primary point of contact for nurses, pharmacists, and other physicians for these patients (i.e., the responding clinician). Their participation in twilight teams does not repeat once they have previously been assigned, so they cannot be re-randomized.

Over the 6-month window, at least 96 interns are expected to be eligible during the proposed 6-month recruitment window. Based on preliminary estimates and consultation with the general medicine service and chief residents, we expect that $\geq 40\%$ of the interns will agree to participate and that therefore at least 36 interns will be included in the study. This rate is highly feasible based on feedback from the clinical leadership engaged in our study team.

Considering the number of potential eligible patients, these interns typically have daily census of 10-20 patients. Each patient is typically admitted for 3-5 days on each general medicine service, so interns typically care for approximately 40 unique patients during their time on the twilight team.

Based on preliminary estimates, $\geq 60\%$ of their patients are older adults, and $\geq 50\%$ will be naïve to either benzodiazepines/sedative hypnotics or antipsychotics. With 36 participating interns, we therefore expect that at least 430 unique patients will be included in the trial analyses (mean: 12 per intern).

We will provide compensation for participation in this trial, which will help ensure retention. Providers will receive \$25 for completing the initial provider survey, \$75 for completion of the simulation intervention or online educational training, and \$50 for completing the follow-up questionnaire. Outside of the brief intervention itself and short baseline and endline (follow-up) questionnaires delivered electronically, there will otherwise be no action required by the participating interns. We have also engaged the chief medical residents in this project, which along with providing access to the scheduling system, will help us track their schedules and help ensure retention.

4.3.1 Inclusivity of study subjects

This study will be conducted on the adult inpatient general internal medicine services at Brigham and Women's Hospital (BWH), which serve a diverse range of patients. As such, we plan to include patients of all race/ethnicities in the analysis, regardless of their primary language. The specific age range (≥ 65 years) was selected because clinical guidelines for the prescribing of high-risk medications of interest are clearer for this age range, and because inappropriate prescribing of these medications is a well-documented issue in the older adult population. Based on the inclusion criteria, we expect that 59.2% of the trial patient participants will be female. In addition, we expect 84.6% will be white, 6.4% will be black or African American, 1.4% will be Hispanic/Latino, 4.2% will be biracial/other, and 3.1% will be Asian/Pacific Islander.

5. Study Interventions

5.1 Therapeutic areas

The focus areas for simulation training will be high-risk medications for older adults, which will be primarily drawn from the outpatient Choosing Wisely recommendations in geriatric medicine but are also informed by the Beers Criteria and other major clinical guidelines.^{33,34} In specific, we plan to focus on the following therapeutic classes: (1) benzodiazepines; (2) sedative

hypnotics (sleep medicines) and (3) antipsychotics. We are also using albumin and blood products as a control, given that they are also high-risk and overprescribed, typically on twilight or evening shifts as patients are admitted to the hospital or are actively decompensating.

5.2 Study interventions

BWH uses 2-week service blocks for its inpatient general medicine evening (twilight) coverage. Prior to the beginning of each block, we will identify the interns assigned to twilight teams (i.e., the primary prescribers on the general medicine service team). We will invite these interns to participate in the study.

- Intervention: Providers in this arm will undergo simulation training at the onset of their 2-week block. The simulation will consist of a one-time, short immersive simulation session at the STRATUS Center for Medical Education at BWH (which is located within the hospital building). We plan to conduct this session with up to 4 interns at the same time, in accordance with social distancing practices at BWH. This simulation session will consist of 1 scenario with two parts of simulated patient experiences with expert facilitators in the simulated hospital rooms to help providers identify when they are in the hot state and their reactions, and work on improving communication skills, differential diagnoses, and alternative therapeutic options. These scenarios are intended to simulate both in-person and virtual interactions that are common in the inpatient setting. During these trainings, we will use behavioral principles like time pressure and increasing cognitive load to simulate a “hot state” environment. After the scenarios, the facilitator will perform a debriefing session for the interns, which will be used to complete the training.
- Control: Providers assigned to the control arm will receive online educational training about other poorly-prescribed medications, including albumin, transfusion, and blood product repletion guidelines. These treatments are often overprescribed on twilight shifts. Receiving education about another high-risk medication will reduce contamination and allow the ability to measure outcomes to other high-risk medications.

These interventions are described in further detail in the “Simulation Scenarios and Online Educational Training overview” document.

5.3 Measures to minimize bias: randomization and blinding

Interns who consent will be randomized in a 1:1 ratio to receive either intervention or control using a random number generator. We plan to conduct stratified randomization based on the service to which the intern is assigned to (GMS, ITU, or Faulkner).

The providers will not be blinded to which arm to which they were assigned, as blinding in the context of an intervention that is intended to motivate action will be infeasible. Physicians randomized to control will not have any way of accessing the intervention. Of note, once on a twilight team, interns are unlikely to rotate back onto a service, so contamination across arms should be minimal. Either way, if this does happen, they will not be re-randomized in the trial. Other ward staff and analysts will be blinded to arm assignment to the extent possible.

6. Study Assessments and Procedures

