BWH and BWFH uses 2-week service blocks for its inpatient general medicine evening coverage, and the service overall consists of 6 day and 8 evening (twilight) teams covering geographically distinct wards at 2 hospital sites with daily censuses of 15-20 patients. These teams typically consist of an attending, a resident, an intern (i.e., 1st year of residency), and medical students. There is no cross-coverage across teams. We will focus on interns from the “twilight” (i.e., evening) teams as they cover the shifts during which the high-risk medications of interest (specifically anti-psychotics, benzodiazepines, and sedative hypnotic “Z-drugs”) are typically first initiated and are also the first point of contact for nurses, pharmacists, and other physicians. Given their stage of training and the nature of their workflow, they are also most prone to make decisions using System 1 thinking.

At the beginning of each rotation, we will identify the interns assigned to the twilight teams (i.e., the primary prescriber and responding clinician on the general medicine service team). We will invite these interns to participate in the study via email invitation. Interns who consent will be randomized in a 1:1 ratio with a random number generator to one of 2 arms: (a) Arm 1: simulation intervention and (b) Arm 2: control (online education) intervention. The unit of randomization will therefore be the intern. Randomizing at the intern level will reduce the possibility of contamination across patients. Providers will receive \$25 for completing the initial provider survey, \$75 for completing the intervention or control assignment (e.g., simulation or online education training), and \$50 for completing the endline (follow-up) questionnaire. Other ward staff will be blinded to arm assignment to the extent possible. Data analysts will be blinded to arm assignment. This is a highly feasible approach used by investigators conducting provider-facing intervention trials at BWH.

[figure not shown]

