Providers assigned to the intervention arm will participate in a short simulation training at the beginning of their 2-week block (planned for their second day). The training will take place at the Neil and Elise Wallace STRATUS Center for Medical Simulation at Brigham and Women's Hospital and will follow all of their recommended and hospital-recommended practices on social distancing, including the learning limits. The training will also be led by [name], hospitalist, Instructor in Medicine, and Assistant Director for Medicine at STRATUS. Based on discussion with [name], the study team, and intern and resident interviews completed in the first phase, it is clear that in-person simulation will have been more effective at creating the stressful situations that could lead to inappropriate prescribing. Moreover, this approach has been used in numerous prior, unrelated trainings conducted by STRATUS and by the general medicine service.

Providers assigned to the control arm will receive online educational training about other poorly-prescribed medications, including albumin, transfusion, and blood product repletion guidelines. This information will be in the form of electronically-delivered links to information already housed and available at BWH, including reviewing BWH guidelines and literature about transfusion reactions. The interns will be asked to answer several clinical questions about optimal prescribing. Albumin and related products are also high-risk medications often overprescribed on twilight shifts. Receiving education about another high-risk medication will reduce contamination and allow the ability to measure outcomes to other high-risk medications.

Follow-up time for trial evaluation will begin on the day in which the interventions are delivered (planned for Day 2 of their service) and will continue until the end of their coverage block on the twilight team. The interventions in both arms will be delivered on the same day, so there will be equal follow-up time. Upon completion of the trial, we will evaluate outcomes, including prescribing and implementation outcomes, using structured EHR data on the patient-level and a follow-up survey of the interns at 2 weeks after randomization.

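### Section 5.3 calls contamination minimal without addressing word of mouth between unblinded interns in mixed-arm blocks, and the plan neither limits nor measures it

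*Combined protocol and SAP*

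**What the plan says.** Section 5.3 gives two reasons for expecting little contamination. One is access: "Physicians randomized to control will not have any way of accessing the intervention". The other is scheduling: "once on a twilight team, interns are unlikely to rotate back onto a service, so contamination across arms should be minimal". It adds that an intern who does return is not re-randomized, and that providers know their arm.

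Section 3.2 names further measures:

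- On team structure: "There is no cross-coverage across teams". The teams work on separate wards at two hospitals.
- On the unit of randomization: "Randomizing at the intern level will reduce the possibility of contamination across patients".
- On the control topic (albumin and blood products): "Receiving education about another high-risk medication will reduce contamination".
- Phase 1 interviewees come from outside the trial service, expressly to avoid contamination.

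Randomization is 1:1 by intern and stratified by service (GMS, ITU or Faulkner). Both arms receive their training on the same day, planned for Day 2. On the session itself, section 5.2 says: "This simulation session will consist of 1 scenario with two parts of simulated patient experiences". Recruitment runs for six months (section 4.3). The endline questionnaire in section 3.8 covers anxiety, stress from uncertainty and satisfaction.

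**The concern.** The inference in section 5.3 does not reach the most obvious route between arms. An intern who rotates back keeps the assigned arm, so a return is not the main way for content to cross. Colleagues in the same block, who know their own assignment, can simply talk. Part of what section 5.2 says is taught (recognizing one's own hot state, communication, alternative treatments) can be described in conversation.

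If controls absorb some of the content, the difference between arms shrinks. Section 2 says the implementation data will help explain a result of no effect. As the questionnaires stand, nothing asks controls whether they heard about the simulation, so that explanation would lack one relevant piece. For a pilot meant to inform larger evaluations, an indication of sharing would also bear on whether to randomize interns or whole blocks next time.

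**Working it through.** **1. Do the stated measures cover talk between interns?**

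| Measure | Route it addresses | Covers word of mouth? |
|---|---|---|
| Controls cannot access the session (5.3) | Attendance | No |
| Interns unlikely to rotate back (5.3) | Repeat exposure | No |
| No cross-coverage, separate wards, two hospitals (3.2) | Shared patients; fewer chance meetings | Only in part |
| Intern as unit of randomization (3.2) | Contamination across patients | No |
| Albumin and blood-product topic for controls (3.2, 5.2) | Content of control materials | No |
| Phase 1 interviewees from outside the service (3.2) | Leakage from the interviews | No |

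**2. How often are the arms mixed in a block?** Inputs: 8 twilight teams (3.2), 96 eligible interns (4.3), 36 participants at 1:1 (4.3, 7.2). This takes one intern per team and simple randomization, an approximation that ignores the service strata.

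- Blocks: 96/8 = 12. Participants per block: 36/12 = 3.
- Both arms present in a block of 3: 1 − 2 × 0.5³ = 0.75. If the number of participants varies as binomial(8, 0.375), this is 0.64.
- Chance that a given co-intern is in the simulation arm: (36/96)/2 = 0.1875.
- Chance that a control has at least one such contact among k co-interns: 1 − (1 − 0.1875)^k. For k = 7 this is 0.766. If contact reaches only 2 or 3 peers (assumption), it is 0.340 or 0.464.

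Contacts trained in earlier blocks are not counted.

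**3. Reproduce the plan's power.** Section 7.2 gives a difference of 0.5, SD 1.1, correlation 0.2, 36 patient-days per intern and 18 interns per arm.

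- Design effect: 1 + 35 × 0.2 = 8.
- Normal approximation, 645 patient-days per arm: effective n = 645/8 = 80.6, power 82.3%. This matches the stated figure of more than 80%.
- t reference with 34 df, 18 × 36 = 648 patient-days per arm: SE = 1.1 × √(2 × 8/648) = 0.173, noncentrality 0.5/0.173 = 2.89, power 80.2%.

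Applying 0.2 to 12 patients per intern instead gives a design effect of 3.2 and 75.0% power (normal), which does not match. The patient-day basis is therefore used below.

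**4. Illustrate dilution.** Let p be the share of controls with a trained contact and f the share of the effect that they take up, averaged over follow-up. The difference becomes 0.5 × (1 − p·f). Neither p nor f is in the documents. Power is on t with 34 df.

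| p | f | Difference | Power |
|---|---|---|---|
| any | 0 | 0.500 | 80.2% |
| 0.340 | 10% | 0.483 | 77.5% |
| 0.340 | 20% | 0.466 | 74.5% |
| 0.464 | 10% | 0.477 | 76.4% |
| 0.464 | 20% | 0.454 | 72.2% |
| 0.766 | 10% | 0.462 | 73.7% |
| 0.766 | 20% | 0.423 | 66.3% |

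**5. Is sharing measured?** Neither questionnaire in section 3.8 has an exposure item. The only dilution toward the null that the protocol names is physician turnover (8.2).

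**The case against.** The best defence is that section 5.3 is right in its own terms: controls cannot attend a facilitator-led session at the simulation center. The trial's premise in section 1 is that education absorbed in a calm state may not prepare clinicians for stressful decisions. A colleague's verbal summary is much closer to that kind of education than to the simulation, so uptake could be small. This stands, and it is why no uptake share can be claimed.

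The protocol also has partial channels already. Section 6.2 collects feedback and issues from interns and staff, and section 7.3.4 explores the effect by month. Either might reveal sharing, but neither is directed at it.

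Three stronger readings are tempting and are not supported:

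- A reader might infer that the protocol considers only rotation back. It does not: it also argues from access, team structure and control topic.
- A reader might infer that the session depends on surprise and so must weaken for later cohorts. Section 5.2 names time pressure and cognitive load, not surprise. That one scenario is reused unchanged for six months is an inference; details are in a separate overview document not available here, which might also contain a do-not-share request.
- A reader might infer that power will fall to a particular value or that a null result would be uninterpretable. The 77% contact figure treats all seven co-interns across two hospitals as contacts, and baseline power is so close to 80% that almost any dilution crosses that line.

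**Conclusion.** The concern holds in a limited form. The reasons in section 5.3 do not support the word minimal with respect to talk between interns, mixed-arm blocks will be usual, and the available text has no step that limits or records sharing. The direction of any bias from sharing with controls is toward the null. Its size is unknown. With 34% to 77% of controls in contact with a trained peer and 10% to 20% uptake, all assumed, the planned difference of 0.5 becomes 0.48 to 0.42 and power falls from 80% to between about 77% and 66%. Prior knowledge among later trainees is a secondary possibility, conditional on the scenario staying the same, and is not quantified. This is a low-priority but nearly costless improvement; it does not call for a change in randomization, sample size or primary analysis.

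**What to change.** - **Section 5.2:** close each debriefing by asking intervention interns not to discuss the scenario or its content with other interns until recruitment ends. If the overview document already contains this, cite it.
- **Section 3.8:** add one endline item per arm. Ask controls whether a colleague described the simulation content to them; ask intervention interns whether they knew the scenario beforehand.
- **Section 7.3.2:** report the answers descriptively by arm next to the primary result. With about 18 interns per arm, do not split them by month.
- **Section 5.3:** state that controls cannot attend the session but may hear of its content from colleagues, and drop the inference from rotation alone.

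The cost is one sentence at debriefing, one item on an existing electronic questionnaire and a rewording. The answers are self-reported and few, so they can help interpret a null result but cannot prove or exclude leakage. Asking controls at endline could itself prompt talk with later cohorts, so the item should be neutrally worded and carry the same do-not-share request. It should be in place before endline data collection begins, because exposure in earlier cohorts would be hard to recover.

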6.1 Baseline data

We will collect baseline data on providers using a brief baseline questionnaire at the time of consent as well as extracted EHR data and data from the Amion scheduling system. This baseline data will be used to assess any potential imbalances in the characteristics of providers despite randomization. The baseline data will include relevant demographic characteristics, such as age, sex, race/ethnicity, and number of months in training. Given the strong potential for characteristics of the study team to influence outcomes, despite randomization, we will also measure characteristics about the interns' team using the Amion scheduling system. Finally, we will also collect patient data from the EHR for eligible patients in follow-up (please see the footnote Section 3.8 for more detail).

6.2 Outcomes

The primary outcome will be measured on the patient-level as the number of high-risk medication doses prescribed per day to eligible patients beginning on the day the intervention arms are delivered to both arms until the end of follow-up. We will only measure doses ordered by the interns in the study. As described above, we will censor follow-up time on when patients transition from the intern's service, when the intern transitions off the twilight service, discharge, or in-hospital

death. The interventions in both arms will be delivered on the same day, so there will be no immortal time bias. Medications that are written pro re nata (PRN) will be treated the same as standing orders for the primary analysis. If patients are eligible to be measured for multiple medication classes (i.e., antipsychotics and benzodiazepines/sedative hypnotics), we will sum the medication doses across the classes.

In secondary analyses, we will only measure doses that are standing orders (i.e., not PRN doses) and doses that were actually administered to patients. We chose to measure this outcome on the patient-day level, because this would enable the fairest comparison between the arms, given that patients have variable lengths of stay and, as a result, the lengths of time under the interns' care. These data will be collected through structured EHR data from MGB paired with data collected from the scheduling system.

